**A Comparative Randomized Controlled Pragmatic Trial of
Neurofeedback and Working Memory Training for Children with
Attention-Deficit/Hyperactivity Disorder: Protocol**

Abstract

Today, the treatment for children and adolescents with Attention Deficit/Hyperactivity Disorder (ADHD) is predominantly pharmacological. However, not all individuals respond to medication or experience side effects. In addition, the compliance and treatment fidelity to medication is sometimes limited, why effective non-pharmacological treatment options are desirable. Neurocognitive training (NCT) methods such neurofeedback (NF) and working memory (WMt) have shown efficacy to treat the primary symptoms of ADHD in non-blinded trials. Still, larger, comparative and blinded pragmatic randomized trials are needed to ensure their efficacy and effectiveness, and to identify an optimal training rationale. Furthermore, little is known about predictors of treatment response to NCTs, such as genetic variants. In this article we present the protocol of a randomized controlled pragmatic trial. Three NCT methods, namely two NF variants, Slow Cortical Potential training (SCP), and Live Z-Score training (LZS), as well as Working Memory Training (WMt) are evaluated against each other and a waiting list control/treatment as usual only group. In a clinical outpatient setting, N = 200 children and adolescents with ADHD aged 9-17 years and common comorbidities are randomized to one of the treatment groups or the inactive control group (n=50/group). The treatment groups (SCP/LZS/WMt) receive a total of 25 highly frequent training sessions (5/week for 5 weeks). A comprehensive assessment comprising ADHD core symptoms, psychopathology, neuropsychology, neurophysiology, quality of life and health related measures are collected pre and post treatment as well as at a 6-month follow-up. Primary outcomes are blinded teacher and unblinded parent ratings as well as self-ratings on the Conners 3 for ADHD. We expect that participants receiving NCT will exhibit improved core ADHD symptomatology compared to waiting list controls. Moreover, we hypothesize that type of NCT (SCP, LZS, WMt) and participant characteristics, such as genetic predisposition, age, IQ, gender, verbal skills, and comorbidity predict patterns of treatment effects the various outcomes.

Key words: ADHD, ADD, comorbidity, attention, treatment, neurofeedback, working memory training, RCT, evidence-based, intervention

Study protocol

Does neurocognitive methods improve AD/HD symptoms? A comparative, randomized and controlled study in naturalistic setting

Background

Attention-deficit/hyperactivity disorder (AD/HD) is a highly prevalent and heterogenic neuropsychiatric disorder affecting about 5% of school-aged children¹. The core symptoms of inattention, impulsivity and hyperactivity in AD/HD causes significant problems in several areas of life, affecting adversely children's development and function and causes clear increased risk of developing mental illness. AD/HD is associated with impairment in school performance, increased risk of accidents and misuse, teenage pregnancy, bullying, social isolation, family conflict, anxiety, hopelessness and depression. Nowadays AD/HD is viewed in a life perspective as the core symptoms, mostly difficulties with attention and impulsivity, follow into adulthood. The prevalence of AD/HD in adults is 3-4%. Long-term follow-up studies show that individuals with AD/HD often fail in studies and at work, have increased risk of criminal behavior, long-term sick leave, and problems with handling finances and household chores. Psychiatric comorbidity is estimated to occur in about 80% of adults with AD/HD², mainly in untreated AD/HD. AD/HD is, therefore, a condition that untreated can lead to serious consequences for the individual and with large subsequent social costs.

International and local guidelines recommend multimodal treatment combining psychosocial and educational interventions with medication³. Most available and commonly used intervention is drug therapy, particularly in the form of stimulants (methylphenidate) which targets behavioral symptoms and has positive effects in the short term, but has limited effect on the long term⁴ and after treatment the core symptoms remains. There are also side effects⁵, and about 20-30% of children and adolescents with AD/HD do not respond to drug therapy⁶, and among those who respond there are still room for improvement. The report by the Swedish Council on Health Technology Assessment⁷ emphasizes the need for evidence-based above all non-medical interventions for AD/HD.

Cognitive learning and training (CLT) methods like neurofeedback (NF) and working memory training (WMt) are non-invasive methods which during the recent years experienced a growing empirical support for improving AD/HD symptoms⁸. NF trains the brains electrical activity through an operant/classical learning paradigm and is supposed to enhance the brains self-regulating ability, i.e. flexibly adapt brain activity to better meet the changing demands of the environment. Previous controlled studies and studies with pre-and post-design has found good results mostly by improving impulsivity and inattention^{9,10,11}. NF has also been demonstrated to induce neuroplastic changes after one session¹² and voluntary control over intrahemispheric functions like the dopamine system¹³. Effects tend to persist after treatment with few side effects (fatigue only after initial training)^{14,15}. WMt focuses on improving working memory functions through challenging exercises in computerized software. Besides encouraging results in enhancing the capacity of foremost visual working memory there has been more sparse evidence that WMt could have beneficial effects on behavioral measures for children with AD/HD^{16,17,18} and questions remain of the nature of the effects and long term effects¹⁹.

Guidelines recommend multimodal treatment combining psychosocial and educational interventions with medication. Compared with psychopharmacological treatment studies there are quite a limited number of studies on alternative treatments for children and adolescents with AD/HD²⁰. CLT's are non-invasive methods and above all NF has shown good preliminary evidence in several international studies in reducing the core symptoms of AD/HD in children, and has encouraging results in contrast to psychopharmacological treatment that the positive effect persists²¹. WMt has promising evidence of improving working memory capacity and that the good effects also can generalize into other functions but there are a clear shortage of studies comparing WMt with other active interventions and controls (Melby-Lervåg, 2012). If the results would be positive then CLT's could broaden the range of treatment for children and adolescents with AD/HD in Sweden. To date there are several different kinds of neurofeedback training options and two mainstream methods are Slow Cortical Potential training (SCPt) and frequency training (Ft) whereas the latter offers more commercially available options. For the clinical validity of this rather extensive training it is of major importance that potential improvements also last. There is a lack of follow-up studies concerning CLTs (Hodgson et al, 2012, Lofthouse et al, 2012, Melby-Lervåg et al, 2012) and the aim of this sub study is to measure long term outcome from CLT methods

Aims and objectives

Primary aim of the study is to evaluate if neurocognitive training improves core symptoms in AD/HD. Key objectives are (i) are there differences in outcome between the different neurocognitive methods, (ii) can we find predictors that differentiate learners from non-learners, (iii) are neurocognitive methods feasible in clinical settings. Additional important research questions are a) if possible improvements generalize to other settings like

school and home environment, b) does effects last six months after training, c) does the training affect the bioelectrical communication in the brain, d) are there more generalized beneficial outcomes as in perceived quality of life, stress in parents, sleep patterns.

Method/design

The KITE study is a randomized, controlled and comparative study conducted in collaboration between Child and Adolescent Psychiatry (BUP) Division in Stockholm and Center of Neurodevelopmental Disorders at Karolinska Institutet (KIND). The study protocol was approved by Ethical Review Board in Stockholm (Dnr.2013/739-31, amendment: Dnr.2013/1729-32). The trial is registered with ClinicalTrials.gov (NCT01841151).

Eligibility and Recruitment

Participants are recruited by referrals from Child Psychiatric Clinics, ADHD-center (Habilitering & Hälsa) and children clinics (Barn- och ungdomsmedicinska mottagningar) in Stockholm County. Self-referrals are also welcome. Parents or legal guardian comes to an information meeting that is held at BUP-KIND. Before entering the study, written consent is obtained from the parent or legal guardian of the participant, and verbal assent for children under 13 or written assent for children 13 years and older. Evaluation about inclusion and exclusion criteria's is made after signed informed consent forms arrives with most recent report of neuropsychiatric evaluation confirming the ADHD diagnose.

A total of n=200 children and adolescents with AD/HD between 9-17 years of age will participate in the study alongside with treatment as usual (TAU) such as drug treatment. The duration for the participant in the study is about 30 weeks a total of; (a) baseline testing, (b) five weeks training/TAU, (c) post testing and (d) six months follow-up testing. Measurements are made with self-, parent- and teacher estimations, psychometric tests and neurophysiological measurements at measure points (a), (c) and (d). Each child and parent or guardian participate in an evaluation session to determine eligibility for the study and to establish a baseline score. To confirm AD/HD diagnosis and to ensure IQ>80 a psychiatric interview is done with parents by Kiddie Schedule for Affective Disorders and Schizophrenia for children of 6-18 years (K-SADS)²² and the participant are tested by Vocabulary and Block Design-tests from WISC IV or WAIS IV from where IQ estimate is calculated.

After referral or self-referral and initial evaluation based on requisitioned report on previously made assessment to establish AD/HD diagnoses the study participants are randomized to four different groups N=50 in each. Two groups of NF (SCP and Ft), WMt group, and the fourth, control group will be measured during treatment as usual (TAU) and will be able to train with self-preferred method after the last measure point. The duration of KITE study is 36 months. After initial screening the duration for participants in the study is approximately 30 weeks a total of; (a) baseline testing, (b) 5 weeks of CLT/TAU, (c) post testing and (d) six months follow-up testing. All the participants attend the study in parallel with TAU, such as drug treatment.

Inclusion criteria

Clinical diagnosis of AD/HD according to DSM-IV-TR and the K-SADS interview, drug naive or under stable medication with stimulants or equivalent for at least 1 month.

Exclusion criteria

IQ <80 (WISC-IV or WAIS-IV), clinically unstable psychiatric condition such as suffering from acute depression, bipolar disorder, severe obsessive compulsive disorder, clinically judged severe self-harming behavior, severe somatic (neurological) disease, or has a very limited knowledge of the Swedish language.

Interventions

Subjects randomized to the training groups, i.e. NF1, NF2 and WMt, comes to the clinic five times per week for five weeks, 25 sessions in total. Each session lasts about 50 minutes.

Two NF methods

NF 1: Slow cortical potential (SCP)

SCP is slower bioelectrical activity in the brain, it is a form of event related potentials (ERPs) and locked in time. It is related to phasic regulation of cortical excitability and apical dendrites of pyramidal cells are believed to be the source of the activity. SCP is characterized of negative and positive shifts lasting from 350(?) milliseconds to several seconds. The negative shift is believed to reflect brain state of allocating attentional resources and increased cortical excitability, and positive shifts reflects inhibition, reduced excitability. In this

study setting children sits in front of a computer screen and are asked to use their brain activity to either move an object up on the screen for negative shift or down for positive. The training segments lasts in total 8 seconds (2 seconds for baseline, 6 seconds of training). One session consists of 36 segments with 50% positive and 50% negative shifts that are trained in random order. Also transfer trials are trained where children has to imagine positive or negative shift according to guidelines presented on the screen. Vertical, horizontal eye movement and eye blinks are recorder and computed before every session and corrected online during training. For segments containing artifacts exceeding.... And ... no feedback is calculated. For closer description see supplement section.

NF 2: Live z-score (LZS)

LZS is thought to compute, view, and process normative z-scores in real time and give feedback to the ongoing electroencephalogram (EEG). The software instantaneous measure different aspects of EEG e.g. relative and absolute amplitude and connectivity measures and give feedback on measured brain activity normative values interpreted to population mean z-score deviations of choice. A metric that is about 0 for the general population, and the trainer decides how many standard deviations and rate of feedback is best to work with. Feedback consists of getting information if the brain meets or not conditions decided by the trainer, e.g. and provides real-time proportional feedback... all feedback is governed by statistical ranges that are defined as plus/minus z-scores or standard deviations.

The training protocol has been design in collaboration with [name], founder of Brainmaster (www.brainmaster.com). It consists of training with 2 channels in two 20 minute sections (first is with following placements; C3 and C4, second part: Fz and Cz), 40 minutes of training in total. Feedback is provided partially by Flashgames and movies with a dimmer (the positive feedback is a brighter screen). For more information see supplement section.

Working memory training (WMt)

KITE study use a computerized software program for working memory training called Memory Quest Flex (www.flexprogram.org). Every session consists of ten different modules with eight (for younger children) or 10 (from 12 years old) different exercises in each. The different exercises stresses on either visual or auditory working memory, and the difficulty level adjusts automatically as a response to individual performance. Various kinds of positive rewards, e.g. oral and collect objects, is provided by the program. After follow-up measure participants in the WMt group are offered NF2 training in the same way as NF2 group are training.

Control

For those randomized to control group are measures collected at the same time points as for the active groups. After final data collection participants in the control group are offered NF training same as the active NF groups have obtained.

Measures

Participants using methylphenidate has a 48 hours wash-out period before measurement.

Primary outcome measures

The primary outcomes for KITE study is changes in AD/HD core symptoms measured by self-, parents- and teacher estimates by full-length Conners 3²³ forms. Conners 3 is a well-studied rating scale aimed to capture manifestations of the behavioural symptoms in AD/HD. It consists of three questionnaires (child, parent and teacher) for children between 6-17 years old.

Secondary outcome measures

Rating scales

*Behavior Rating Inventory of Executive Function (BRIEF)*²⁴ is used for parents and teachers to fill to identify dysexecutive functioning and possible improvements with neurocognitive training. It is an [86-item questionnaire](#).

KIDSCREEN-27^{25,26}; is a self-report questionnaire consisting of 27 items applicable to children between 8-18 years about perceived quality of life (QoL). Items are scored on a five-point scale; higher scores indicate better experienced QoL. The KIDSCREEN-27 has been shown to have robust psychometric properties²⁷.

*The Swedish Parenthood Stress Questionnaire (SPSQ)*²⁸ is developed from Parenting Stress Index (PSI)²⁹ and consists of 35 questions divided into five domains. The aim is to detect perceived stress related to parenthood.

*Diet and exercise questionnaire*³⁰; Swedish National Food Administration's published diet and exercise questionnaire for adults has been slightly adjusted to suit children, and parents fills it at the first measure point.

Sleep questionnaire – simple schedule of registration sleep onset, time and perceived sleep quality for one week (seven nights) is filled one week before, after training and at the follow-up time point.

Cognitive measures

*Conners CPT II*³¹: is a task-oriented computerized continuous performance test. It measures inattentiveness, impulsivity, sustained attention and vigilance.

Find the phone task: Is a computerized test where the task is to avoid selecting several times the phone that already has rung among many phones on the screen. The number of times an already rung phone is selected is used as a measure of deficits in the working memory. The task is similar to the spatial working memory task in Cambridge Neuropsychological Test Automated Battery (CANTAB³²).

Working memory; forward and backward digit and block span subscales from the WISC-IV³³ or WAIS-IV³⁴ were administered. The dependent measure is the level where participant fails to correctly repeat digits or block on two consecutive trials at one level of difficulty.

IQ; IQ estimate³⁵ is calculated from the subtests vocabulary and block design in WISC-IV or WAIS-IV.

*Tapping*³⁶ This is a computerized auditory task. Every 1,200ms a tone is presented, and the child has to tap at the same pace by pressing right mouse button. After 15 cued trials the child is asked to continue tapping at the previously cued rate for 41 uncued trials. Within-subject standard deviation will be calculated of the variability in tapping.

*Duration Discrimination*³⁷ Two unfilled intervals (target and comparison) defined by two brief tones (50 milliseconds; 1000 Hz) before and after are presented to the child. The task is to discriminate between longer and shorter, target interval (400 milliseconds, ms). The participant responds by pressing left mouse button if the first tone is longer and right button if they think the second one is longer. The trial intervals are separated by 800 ms and inter-trial interval is 1000 ms. The target interval shifts randomly from first to second place, and the longer is adjusted up or down in 10 ms increments depending on the accuracy of response. An adaptive procedure was used to track 80% accuracy³⁸ and after six reversals of direction the test ended. The dependent measure is the average of the last five reversal values.

*Time anticipation*³⁹. A computerized task where the child has to beam oxygen to a spaceship to save the crew. In the beginning the target ship becomes visible at the same rate for the first trials and the child has to press a button. After ten trials the child has to estimate when the so called cloaked or invisible ship appears at the same interval as on the uncued, visible trials. Feedback is given in both visible as invisible trials. In the first block the response rate was every 400 ms and on the second block 2000 ms. the dependent measure is calculated as the mean percentage of responses made before the ally arrived (i.e. too early responses).

Biomarkers

Quantitative electroencephalogram (QEEG) measured through 21 electrodes, placed according to international 10-20 system. Three minutes eyes open, three minutes eyes closed.

Event-related potentials (ERP) is neuronal processes underlying measurable overt behaviour such as speed and accuracy of processing information. ERPs provides direct measure of brains covert activity and its precise timing, specifically preparatory and inhibitory processes.

- P300 measured from central location (Cz) and is seen as an index of neurophysiological response inhibition (or no-go). Reduced P3 amplitude to cues in CPT-OX test is associated with resource allocation and covert attentional orienting is the most consistent neurophysiological deficit in childhood AD/HD⁴⁰.

- Contingent Negative Variation (CNV) measured centrally Cz is indication of preparatory processes in the brain, reduced amplitudes indicate deficits in time processing, motor and non-motor preparation in childhood AD/HD⁴¹
- Error-related negativity (ERN) recorded from CFz⁴² when participants make errors in the flanker task ERN presents as a negative detection approximately 50-100 ms following the erroneous response. It is thought to reflect error-related brain activity namely individual's ability to monitor behaviour. Deficits in executive functioning i.e. response monitoring is one hallmark in AD/HD

Flankers test which is a kind of reaction time task and where the subject has to respond as quickly as possible, while avoiding errors. The participants are required to indicate the direction of a central target in an array of three stimuli. *Continuous performance test, CPT-OX* consists of 400 letters presented briefly (150ms) every 1,65 s in a pseudorandom sequence at the centre of a computer monitor. Letter "O" is the cue and initiate 40 cue-target i.e. 'O' followed by letter 'X' (go condition) or 40 cued non-target (O followed by different letter than X, no-go condition).

Randomization

Random list of numbers. The date when consent form has arrived.

Statistical analysis

We expect that participants receiving NCT will exhibit improved core ADHD symptomatology and secondary and exploratory outcomes compared with waiting list controls. Moreover, we hypothesize differing effects of Cognitive training in ADHD type of NCT (SCP, Lzs, WMt) based on the participant characteristics (e.g. genetic predisposition, age, IQ, gender, verbal skills, and comorbidity) will predict patterns of treatment effects on the various outcomes. The sample size calculation refers to the three primary outcome endpoints: change in Conners 3 total scores and subscales for parent, self-report, and blind teacher ratings between baseline and follow-up assessment, in the Intention to Treat (ITT) sample. MANOVA for repeated measures (three measurement points, withinbetween subjects' interactions, posthoc tests) will be used for the statistical analysis for the RCT study. Based on available evidence about NCT efficacy medium effects for the primary outcomes are expected. With N=200 (n=50 SCP vs. n=50 Lzs vs. n=50 WMtr vs. n=50 TAU only controls) and alpha=5%, the power (1-beta) is >99% for medium effects (G Power 3.1.7). All data provided for the participants will be included in the analyses. Data will be tested for normality and homogeneity of variance. To verify that the treatment group and control groups are comparable for continuous and categorical demographic variables at pretreatment, a series of independent-samples t-tests and chi-square tests will be conducted. As for primary outcomes, analyses for secondary outcomes will be conducted according to ITT principles. To analyse for the significance of potential factors predicting outcomes (age, IQ, language abilities, gender, comorbidity, genetic variants) in the active NCTs training groups, these are analysed using a logistic regression to explain dichotomized (by median-split) Conners 3 outcomes as the dependent variable.

Adverse events

Potential adverse events will be continuously monitored with Paediatric side effect checklist (P-SEC⁴³). P-SEC is commonly used in monitoring possible side effects of stimulants. Before training and every 5th training session the parents are interviewed or asked to fill in the P-SEC. For every participant in the active groups are a total of six P-SEC followed through. For the control group P-SEC is rated at pre- and post-measure points and once during the active groups training period. Spontaneous remarks of possible adverse events are thoroughly noted in participant's journals. As the study is conducted within newly established research child psychiatric out-door unit the participants are protected through patient insurance.

Discussion

The project aims to optimize brain functioning to facilitate among other things the ability to focus and maintain attention, controlling impulsive behavior and activity level that are the core difficulties in AD/HD. An important role is also giving access to evaluated non-pharmacological methods with scientific basis to children and adolescents with AD/HD. We know today that untreated AD/HD gives suffering and have far-reaching consequences at the individual, group and society level. There is a need for proven interventions for children and adolescents with AD/HD in addition to drug treatment (SBU, 2012⁴⁴). Some do not respond or respond only marginally to drug treatment, others do not want medications that have side effects and that the core problems

remain after the medical treatment has ceased. CTL are non-invasive methods where NF has shown good preliminary evidence in several international studies in reducing the core symptoms of AD/HD in children and in contrast to psychopharmacological treatment the effect seem to persist foremost of NF training. The study is the first of its kind in Sweden and will be conducted in naturalistic clinical environment that ensures external validity to the study results. If the results show effectiveness CLT methods could broaden the range of treatment for children and adolescents with AD/HD in Sweden. In the long term it can lead to decreased suffering, increased function in everyday life, education and work, and quality of life for the individual patient and their family, and reduced social costs.

Trial status

The first participant enrolled in the study in August 2013.

¹ Polanczyk et al. (2007). Am J Psychiatry, 164, 942-948

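### Does the plan let children be allocated before eligibility is confirmed and baseline Conners 3 is rated?

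*Combined protocol and SAP*

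**What the plan says.** The Randomization section consists of two fragments: "Random list of numbers. The date when consent form has arrived".

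The order of events has to be pieced together from other sections.

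- **Eligibility and Recruitment, on consent.** The check of inclusion and exclusion criteria "is made after signed informed consent forms arrives with most recent report of neuropsychiatric evaluation confirming the ADHD diagnose".
- **Same section, on the evaluation session.** "Each child and parent or guardian participate in an evaluation session to determine eligibility for the study and to establish a baseline score". On its content: "To confirm AD/HD diagnosis and to ensure IQ>80 a psychiatric interview is done with parents", together with two Wechsler subtests for the IQ estimate.
- **Same section, on allocation.** After referral and "initial evaluation based on requisitioned report on previously made assessment to establish AD/HD diagnoses the study participants are randomized to four different groups".
- **Same section, on the schedule.** "After initial screening the duration for participants in the study is approximately 30 weeks a total of; (a) baseline testing".
- **Inclusion criteria.** "Clinical diagnosis of AD/HD according to DSM-IV-TR and the K-SADS interview". An IQ below 80 is an exclusion criterion.
- **Abstract, on raters.** "Primary outcomes are blinded teacher and unblinded parent ratings as well as self-ratings on the Conners 3 for ADHD".

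The Statistical analysis section makes change in Conners 3 from baseline to follow-up the primary endpoint in the intention-to-treat sample. It says that all data provided will be analysed, and it plans a repeated-measures MANOVA over three time points. Its pretreatment comparison of groups names demographic variables only. Enrolment began in August 2013 (Trial status).

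**The concern.** The one sentence that places something before randomisation mentions only a review of an existing report. The trial's own K-SADS interview and IQ estimate, either of which can make a child ineligible, belong to a separate session with no stated position relative to allocation. The Randomization section mentions only one date, the arrival of consent, and the eligibility check comes after that. Read together, these passages can suggest allocation first, then eligibility and baseline.

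Two things would be at stake. First, a child found ineligible after allocation might be dropped, and the intention-to-treat set is named without a definition. Second, the baseline value enters every primary change score. Parents are unblinded and self-ratings are not called blinded, so arm knowledge at baseline could shift two of the three primary outcomes, either imitating a benefit or hiding one. Teacher ratings are described as blinded and should not be affected. The comparison of groups at pretreatment would not look at Conners 3.

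**Working it through.** **1. Does the text fix an order?** Three points bear on it.

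- Consent arrival appears in the Randomization section without a verb. It can mean that a child is allocated on that date, or that the date sets the order in which children take numbers from the list. The text does not decide between these.
- The evaluation session serves to determine eligibility, K-SADS is an inclusion criterion, and those randomised are called study participants. Baseline testing is the first schedule item, after initial screening. This fits screening and baseline first.
- The sentence on randomisation names only the report-based evaluation as preceding it. It does not say that the session comes later.

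The order is open, with some lean towards screening first. Nothing instructs staff to allocate before the session.

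**2. The plan's own figure.** The stated power is above 99% for medium effects with 200 children. Taking medium as f = 0.25 (assumed), 4 groups and 3 times, noncentrality is f²·N·3/(1−r).

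- r = 0: 0.0625 × 200 × 3 = 37.5, power 0.9989.
- r = 0.5: 37.5/0.5 = 75, power above 0.9999.

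The figure reproduces and does not depend on the order of allocation.

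**3. Exclusions.** No failure rate is given. Each 1% is 2 of 200 children. Referral with a report confirming the diagnosis should keep K-SADS failures low.

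**4. A baseline shift from knowing the arm.** From the plan: 50 per arm, 4 arms, 3 times, alpha 5%. Assumed: unit SD at each time, equal correlation r = 0.5, shift s at baseline in one arm, no true effect. Let k be the fraction of s still present at both later visits. Only the part that differs over time, e = s(1−k), enters a change score or the interaction.

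- Interaction: noncentrality = 50·e²·(3/4)·(2/3)/(1−r) = 50·e², tested on F(6, 392).
- One change-score contrast: SE = √(2(1−r))·√(2/50) = 0.20; noncentrality = e/0.20, t on 98 df.

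| s | k | e | Interaction noncentrality | Interaction type I error | Contrast type I error |
|---|---|---|---|---|---|
| 0.1 | 0 | 0.10 | 0.5 | 7.0% | 7.9% |
| 0.2 | 0 | 0.20 | 2.0 | 14.4% | 16.8% |
| 0.1 | 0.5 | 0.05 | 0.125 | 5.5% | 5.7% |
| 0.2 | 0.5 | 0.10 | 0.5 | 7.0% | 7.9% |
| either | 1 | 0 | 0 | 5% | 5% |

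At k = 0, letting r run from 0.3 to 0.7 gives 6.4% to 8.5% (s = 0.1) or 11.4% to 22.3% (s = 0.2) for the interaction.

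In the masking direction, with an assumed true benefit of 0.5 SD and r = 0.5, contrast noncentrality is (0.5 − e)/0.20. Power is 70% with no shift. At k = 0 it is 51% (s = 0.1) or 32% (s = 0.2). At k = 0.5 it is 61% or 51%.

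The larger figures therefore require a shift that is present at baseline and gone at both later visits. Parents stay unblinded throughout, so some persistence is plausible, but the documents give no value for k. A later shift in the opposite direction (negative k) would raise the figures above the k = 0 rows.

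**5. Would testing baseline Conners 3 help?** For 50 against 50, SE = √(2/50) = 0.20, so noncentrality is 0.5 or 1.0 and the test would detect the shift 7.9% or 16.8% of the time. Adding it to the pretreatment comparisons would gain little.

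**The case for a change.** The strongest reply is that concealment is missing on either reading. Even if screening came first, the plan does not say who held the list or whether the next assignment could be foreseen, and a purpose clause about eligibility is not a stated order. The Randomization section carries no redaction mark, so the silence belongs to the plan. Writing down the order, the list holder and the definition of intention to treat would cost a few sentences and no extra visit.

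Most of that stands as a comment on reporting. A reader cannot verify allocation integrity from this document, and the trial report should state the order, the concealment method and any exclusions after allocation by arm. What does not stand is the step from silence to a faulty procedure. If eligibility and baseline already precede allocation, stating so alters nothing that is done. New wording cannot repair assignments already made since enrolment opened. Intention to treat ordinarily means all randomised children, and with the promise to include all data, dropping a randomised child would depart from the plan. Permuted blocks would answer an imbalance for which there is no evidence.

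**Conclusion.** The concern does not call for a change to the plan. The Randomization section is too brief to show when allocation occurs or how it is concealed, but no stated rule is shown to give a wrong result. The text is compatible with eligibility and baseline first. Analysts following ordinary practice would screen, collect baseline ratings, then allocate, and would analyse every randomised child.

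The size of any bias is unknown. For a single parent or self outcome, the illustrations run from no inflation (5%) to 14.4% for the interaction and 16.8% for one contrast at r = 0.5. That upper end assumes allocation came first, families knew the arm, baseline moved by 0.2 SD, and the movement had vanished by both later visits. None of these is established by the documents. The range also leaves out a later shift in the opposite direction, which would enlarge the distortion. The conclusion would change if records showed that children were allocated before eligibility or baseline and then excluded, or that the list was open to those enrolling them.
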